3.2 CLINICAL ASSESSMENTS

3.2.1 *Efficacy*

3.2.1.1 *Clinical Worsening*

Clinical worsening will be assessed continuously from randomization until the subject's last study visit. All clinical worsening events will be reviewed by the sponsor Medical Monitors. To ensure subject eligibility for the open-label extension study (TDE-PH-311), subjects should remain on study drug until the clinical worsening event has been reviewed and confirmed by the Medical Monitor unless the Investigator feels it is medically necessary to discontinue study drug for the welfare of the subject. Clinical worsening (adjudicated) is defined as the occurrence of any one of the following clinical worsening (morbidity or mortality) events:

- Death (all causes)
- Hospitalization due to worsening PAH defined as:
 - Non-elective hospitalization lasting at least 24 hours in duration caused by clinical conditions directly related to PAH and/or right heart failure; or
 - Lung or heart/lung transplantation; or
 - Atrial septostomy
- Initiation of an inhaled or infused PGI₂ for the treatment of worsening PAH
- Disease progression (all criteria required):
 - A decrease in 6MWD of at least 15% from Baseline (or too ill to walk) directly related to PAH progression with other co-morbidities ruled out, confirmed by two 6MWTs performed on different days*
 - Worsening of PAH symptoms, which must include either
 - An increase in functional class from Baseline *or*
 - Appearance or worsening of symptoms of right heart failure since Baseline
- Unsatisfactory long-term clinical response (all criteria required)
 - Randomized to receive study drug for at least 24 weeks
 - A decrease from Baseline in 6MWD at Week 24 and beyond at two consecutive visits on different days*
 - Sustained WHO Functional Class III or IV symptoms for at least 24 weeks consecutively

*Confirmatory 6MWTs should be conducted within 30 days of the qualifying decrease in 6MWD; however, confirmatory 6MWTs occurring outside of this window will still be considered to have met the definition of clinical worsening and sent to the adjudication committee for review.

Once a clinical worsening event occurs, it must be entered on the specified form in the electronic case report form (eCRF) and should be submitted within 48 hours after the event becomes known to the Investigator or designee. When the form is submitted, the sponsor Medical Monitor will review the event and correspond with the Investigator and site, as appropriate. Although subjects may be discontinued from the study for medical necessity at any time, subjects should not be discontinued for a clinical worsening event until the event has been reviewed by the Medical Monitor. Once the clinical worsening event has occurred, the subject will then complete the Study Drug Termination visit assessments.

Clinical worsening events that meet the definition of a serious adverse event (SAE) will follow the same reporting requirements as all SAEs (Section 9.3). These events must also be entered on the specified form in the eCRF.

In addition to the Medical Monitor reviewing all clinical worsening events as and when they occur, an independent adjudication committee will review all clinical worsening events periodically throughout the study (Section 10.8).

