Each 6MWT conducted after Randomization should be documented and compared to the subject's Baseline 6MWD. If a subject has a decrease of 15% or more in walk distance compared to Baseline, a second confirmatory 6MWT should be performed on a different day to assess for clinical worsening (confirmatory 6MWTs should be conducted within 30 days of the qualifying decrease in 6MWD; however, confirmatory 6MWTs occurring outside of this window will still be considered to have met the definition of clinical worsening and sent to the adjudication committee for review). If the second 6MWT also shows at least 15% decrease in 6MWD as compared to Baseline and the subject has either worsened in WHO Functional Class compared to Baseline or has the appearance or worsening of symptoms of right heart failure since Baseline, the subject will meet the 'disease progression' definition of clinical worsening and should follow steps as outlined in Section 3.2.1.1. Prior to exiting the study, the Study Drug Termination visit assessments should be conducted at the time the decision is made to discontinue study drug (prior to down titration). For subjects who meet the definition of clinical

worsening for disease progression due to at least a 15% decrease in 6MWD from Baseline, the date of the clinical worsening event will be the date of the second confirmatory 6MWT.

After the first 24 weeks of study participation, if a subject has any two consecutive 6MWTs on different days that demonstrate any decrease in 6MWD from Baseline accompanied with sustained WHO Functional Class III or IV symptoms for at least 24 weeks, consecutively, the subject will meet the clinical worsening definition of unsatisfactory long-term clinical response and should follow steps outlined in Section 3.2.1.1.

Details regarding the conduct of the 6MWT are described in Section 15.1.

3.2.1.3 *Borg Dyspnea Score*

The Borg dyspnea score will be assessed following each 6MWT. The Borg dyspnea score is a 10-point scale rating the maximum level of dyspnea experienced during the 6MWT (Section 15.1). Scores range from 0 (for the best condition) to 10 (for the worst condition).

3.2.1.4 *WHO Functional Classification*

The WHO functional classification for PAH (Section 15.2) will be assessed at Baseline prior to starting study drug and at all subsequent scheduled study visits, and every time the 6MWT is performed for purposes of assessing clinical worsening status.

3.2.1.5 *N-terminal pro-BNP*

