## 8.5 DERIVED AND TRANSFORMED DATA

Time to Clinical Worsening will be derived as follows:

Parameter	Scenario	Formula	Status
Time to Clinical Worsening (weeks)	Subjects with clinical worsening event reported during the study that is adjudicated/confirmed	= (Worsening date – Randomization date)/7 Note: for subjects with clinical worsening due to worsening 6MWD, the clinical worsening date is date of the second/confirmatory 6MWT	0 (event)
	Subjects who died during the study	= (Death date – Randomization date)/7	0 (event)
	Subjects with clinical worsening event reported during the study that is adjudicated as not meeting the clinical worsening event criteria by the adjudication committee	For analysis of investigator reported clinical worsening event: = (Worsening date – Randomization date)/7	0 (event)
		For analysis of adjudicated clinical worsening event: = (Last assessment date – Randomization date)/7	1 (censored)
	Subjects without clinical worsening event during the study	= (Last assessment date – Randomization date)/7	1 (censored)
Subjects discontinued from the study prematurely that did not have a clinical worsening event	= (Last assessment date – Randomization date)/7	1 (censored)	

For subjects with clinical worsening due to the decrease from Baseline in 6MWD, confirmatory 6MWT should be conducted. The event time is based on the date of the

confirmatory 6MWT. As a sensitivity analysis, the event time based on the date of the first reported 6MWT will also be performed.

Hemodynamic parameters will be derived as follows:

Parameter	Formula
Cardiac index in L/min/m 	= cardiac output (CO) Fick / body surface area (BSA)
Systemic vascular resistance (SVR) in dynes*sec/cm 	=80 * (systemic arterial pressure mean [SAPm] – right atrial pressure mean [RAPm]) / CO Fick
SVR index (SVRI) in dynes*sec/cm  /m 	=80 * (SAPm – RAPm) / cardiac index
Pulmonary vascular resistance (PVR) in dynes*sec/cm 	=80 * (Pulmonary artery pressure mean [PAPm] – Pulmonary capillary wedge pressure mean [PCWPm]) / CO Fick
PVR Index (PVRI) in dynes*sec/cm  /m 	=80 * (PAPm – PCWPm) / cardiac index

Electrocardiogram parameters will be derived as follows:

Parameter	Formula
QTc (Bazett)	$= QT / \sqrt{\frac{60}{HR}}$
QTc (Fridericia)	$= QT / \sqrt[3]{\frac{60}{HR}}$

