#### ***10.1.1.2 Primary Efficacy Analyses***

Data on the Clinical Worsening Assessment page of the eCRF will be used in determining clinical worsening status. Investigator-reported clinical worsening events will be reported directly from the eCRF data, regardless of the outcome of the adjudication committee review. An independent adjudication committee will be utilized to adjudicate all investigator-reported clinical worsening events. Adjudicated clinical worsening events will be reported using data received from the adjudication committee.

Subjects who discontinue study drug for reasons other than clinical worsening will be censored at the time of discontinuation of the study drug. Non-fatal clinical worsening events that occur more than 7 days after permanent study drug discontinuation will not be included in the summary and analysis of clinical worsening events. However, all deaths within the study follow-up period (30 days after the last study drug dose) will be included as clinical worsening events. Time to clinical worsening will be summarized by treatment group using product-limit estimates calculated by the Kaplan-Meier method, and displayed graphically as Kaplan-Meier curves. A tabular summary of this analysis will include the number of subjects at risk (sample size), estimated median duration, and a 95% confidence interval for the median duration for each treatment group.

For the primary efficacy analysis of time to adjudicated clinical worsening, the log-rank test adjusted for the type of background therapy (PDE5-I or sGC stimulator versus ERA) and the Baseline 6MWD ( $\leq 350$  meters versus  $> 350$  meters) will be used to calculate the p-value for treatment differences in the ITT Population.

The SAS Procedure LIFETEST will be used. The pseudo SAS statements are listed below:

```
proc lifetest;
  time TimeToWorsening*Censor_Status(1);
  strata BGTX B_6MWD / group=Treatment test=all;
run;
```

where BGTX variable denotes the background therapy and B\_6MWD denotes the Baseline 6MWD category ( $\leq 350$  meters versus  $> 350$  meters).

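### A 6MWD fall first measured on drug can drop out of the primary analysis if drug is permanently stopped and the confirming walk comes more than 7 days later

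*Protocol*

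**What the plan says.** Four rules meet here.

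- **Confirmation window.** Protocol 2.1, 3.2.1.1 and 3.2.1.2.3 set a target: "Confirmatory 6MWTs should be conducted within 30 days of the qualifying decrease in 6MWD". It is not a limit, because "confirmatory 6MWTs occurring outside of this window will still be considered to have met the definition of clinical worsening", subject to adjudication.
- **Event date.** Protocol 3.2.1.2.3 says that for disease progression "the date of the clinical worsening event will be the date of the second confirmatory 6MWT". SAP 8.5 agrees: "for subjects with clinical worsening due to worsening 6MWD, the clinical worsening date is date of the second/confirmatory 6MWT".
- **Cut after drug stop.** SAP 10.1.1.2 says: "Non-fatal clinical worsening events that occur more than 7 days after permanent study drug discontinuation will not be included". Subjects who stop drug for reasons other than clinical worsening are censored at the stop. The derivation table in SAP 8.5 has no such limit and codes any confirmed, adjudicated event as an event.
- **Stopping before confirmation.** Protocol 3.2.1.1 asks subjects to stay on drug until the Medical Monitor has confirmed the event, "unless the Investigator feels it is medically necessary to discontinue study drug for the welfare of the subject". Protocol 4.3.1 adds a second route: before Week 24, starting a second oral PAH therapy ends study drug, while the subject is encouraged to attend visits up to Week 24.

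SAP 8.5 also plans a check: "As a sensitivity analysis, the event time based on the date of the first reported 6MWT will also be performed".

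**The concern.** The 7-day cut is applied to a date that may lie 30 days or more after the deterioration was first measured. A subject can show a fall of 15% or more while on drug, stop drug permanently, have the fall confirmed and adjudicated, and still be counted as event-free up to the stop. That censoring comes at the moment the subject is getting worse, so it is informative. If it is more frequent in one arm, it biases the hazard ratio.

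The SAP is also not fully determined. A programmer working from the 8.5 table keeps such an event, and one working from 10.1.1.2 drops it. The planned first-walk-date analysis does not settle this. It does not say which date the 7-day rule uses there, it is missing from the list in SAP 10.1.1.3, and no table title in SAP 16.1 identifies it. If its 7-day rule uses the first-walk date, it changes which events count as well as when they occur, and cannot be read as a pure timing check.

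**Working it through.** **1. The plan's own figure.** Inputs from Protocol 10.2: 205 events, hazard ratio 0.62, two-sided 0.05 overall and 0.044 at the final analysis. Allocation is 1:1 (Protocol 5.2). Schoenfeld power is Φ(|ln HR|·√d/2 − z), with |ln 0.62| = 0.478.

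- At 0.05: 0.478 × 14.318/2 − 1.960 = 1.462, which gives 92.8%.
- At 0.044: 3.422 − 2.014 = 1.408, which gives 92.0%.

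Both agree with the stated figure of at least 90%.

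**2. The rule in days.** Let Day 0 be the first qualifying walk, S the day of permanent stop and C the day of the confirming walk. Under SAP 10.1.1.2 the event counts only if C − S ≤ 7. If the stop is decided at the first walk (S = 0), Days 1 to 7 count and Days 8 to 30 do not, although the protocol accepts all of them.

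**3. Share lost among such subjects.** Assume C is equally likely on each of Days 1 to 30. The share lost is (30 − (S + 7))/30.

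- S = 0: 23/30 = 77%
- S = 7: 16/30 = 53%
- S = 14: 9/30 = 30%

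The result depends on how quickly sites confirm. For the same three stop days, a window of Days 1 to 14 gives 50%, 0% and 0%. A window of Days 1 to 60 gives 88%, 77% and 65%.

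**4. Effect on power.** The documents do not say how many subjects stop drug between the two walks, so the number lost is an assumed range. Nor do they say whether events excluded by the 7-day rule count toward the 205 that end the trial. If they do, at 0.044:

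- 5 lost: 0.478 × √200/2 − 2.014 = 1.366, which gives 91.4%.
- 10 lost: 0.478 × √195/2 − 2.014 = 1.324, which gives 90.7%.

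Freedman's formula runs about one point lower (90.4% and 89.6%). For 90% power at 0.044 the trial needs 191 events (Schoenfeld) or 198 (Freedman), so 14 or 7 can be lost first.

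**5. Effect of unequal loss (illustration).** Take a true hazard ratio of 1 with 102.5 events per arm. Losing 10 events in one arm and 5 in the other gives an event ratio of 92.5/97.5 = 0.949, and z = ln(0.949) × √(190/4) = −0.36. The two-sided error at the 0.044 level is then about 0.058. If the arms are swapped, the ratio is 1/0.949 = 1.05 with the same error.

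**The case against.** The protocol limits the gap. Subjects are asked to stay on drug until review. Protocol 7.4 requires a 6MWT before down-titration, which can confirm an earlier fall if it is on a different day. After a stop for reasons other than worsening, visits are encouraged only to Week 24; after that, Protocol 3.5 plans only a survival contact at about 30 days. One sentence in Protocol 4.3.1 even has a subject who starts a second oral therapy leave the study at any time, which conflicts with the Week 24 provision in the same section. So off-drug confirming walks may be few.

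An off-drug walk is also not a clean confirmation. Table 3-1, footnote d, requires every post-randomization walk 3 to 6 hours after the last dose, and the synopsis warns that sudden dose reductions may worsen PAH. SAP 8.3.1 and 10.1.1.3 already plan analyses that count early termination as an event.

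Most of this stands, and it limits how often the gap matters. It does not close it: no text exempts a fall first measured on drug, a fall first seen at the termination visit cannot confirm itself, and the early-termination analyses count all dropouts, or all adverse-event dropouts, without isolating these subjects.

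Four stronger readings are tempting and not supported.

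- **The protocol and SAP disagree on the event date.** They agree; the mismatch is between that date and the 7-day cut.
- **Every such fall is lost.** Confirmation within 7 days of the stop, or another qualifying event in time, keeps the subject in.
- **The rule removes the sickest.** PAH hospitalization and starting an inhaled or infused prostacyclin need no second walk, and deaths count to 30 days after the last dose.
- **More UT-15C events are lost, because a lower dose means a shorter taper.** Apply the dose-reduction guidance in Protocol 6.1 to 3 mg and 6 mg, with the clock running from the last dose. The fastest step (0.25 mg per 12 hours) ends dosing on Day 6 or 12, with 17/30 = 57% or 11/30 = 37% lost. The slowest (0.125 mg per 24 hours) ends on Day 24 or 48, with none lost from either. Protocol 6.1 leaves the taper at permanent stop to the Investigator. The doses of 3.1 and 6.1 mg that suggest the contrast come from an earlier 16-week twice-daily trial.

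**Conclusion.** The point holds in a limited form. Followed exactly, SAP 10.1.1.2 can turn a confirmed, adjudicated event into a censoring when three conditions coincide: a permanent stop before confirmation, a confirming walk more than 7 days after it, and no other qualifying event in time. The 8.5 table and 10.1.1.2 give different answers for that subject.

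Within this group the loss may be 30% to 77%, on the uniform 30-day assumption and stops on Days 0 to 14. The size of the group is not in the documents and is probably small. Power is not the issue: it stays at about 91% (Schoenfeld) with 5 to 10 events lost. What matters is informative censoring in the primary endpoint, with a direction by arm that cannot be settled from the documents. The repair costs little and should be made before unblinding.

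**What to change.** - **SAP 10.1.1.2.** For walk-based events, apply the 7-day test to the date of the first qualifying 6MWT. Count the event if that walk was on drug or within 7 days of the last dose and the fall was later confirmed and adjudicated.
- **Dating.** Keep the confirmatory date for events confirmed inside the 7-day cut. For those confirmed after it, use the date of the first qualifying walk. With the confirmatory date, follow-up would run past drug stop only for subjects who later confirm, while the others are censored at the stop.
- **Sensitivity analysis.** Use the same event set in the first-walk-date analysis, so that only the date changes, and list it in SAP 10.1.1.3 and 16.1.
- **Consistency.** Align the SAP 8.5 table with 10.1.1.2, and state whether events excluded by the 7-day rule count toward 205. Reconcile Table 3-1, footnote d, with the acceptance of late confirmation in Protocol 3.2.1.1 and 3.2.1.2.3, for walks made after drug stop.

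The cost is a few sentences in the SAP and a change to the event derivation; it needs both walk dates, which the SAP's own first-walk analysis already requires. The downside is small: a few events will rest on an off-drug confirming walk and be dated differently from Protocol 3.2.1.2.3. The SAP should say so.

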3.2.1.2 Six-Minute Walk Test

The intent of the 6MWT is to evaluate exercise capacity associated with carrying out activities of daily living. All 6MWTs will be conducted by qualified, trained personnel in a designated 6MWT area which meets the requirements as described in Section 15.1. Prior to the start of each 6MWT the subject should rest (seated) for at least 5 minutes.

3.2.1.2.1 Practice Six Minute Walk Test

All subjects must have a documented 6MWT conducted at the study site on the course intended for use during the study. If no previous 6MWT has been performed at the study site, a practice 6MWT must be conducted at least 1 day prior to the Randomization 6MWT for applicable subjects.

3.2.1.2.2 Baseline Six Minute Walk Test

A Baseline 6MWT must be performed prior to initiation of study drug and should be conducted on the day of randomization. The Baseline 6MWT must be conducted no earlier than 1 day following the practice 6MWT, for applicable subjects. Once the Baseline 6MWT has been

conducted, the site will enter the subject's six-minute walk distance into an interactive voice or web response system (IVRS/IWRS). IVRS/IWRS will confirm to site personnel the subject's eligibility to participate in the study based on 6MWD, and if eligible, randomize the subject into a treatment group and allocate appropriate study drug.

3.2.1.2.3 *Treatment Six-Minute Walk Tests*

6MWTs will be conducted at Weeks 4, 8, 12, 24, and every 12 weeks thereafter. The 6MWT should be conducted 3 to 6 hours following the last dose of study medication. Subjects receiving supplemental oxygen during the Baseline 6MWT must continue to receive the same flow rate and mode of oxygen therapy at all subsequent 6MWT assessments; any changes in oxygen therapy administration should be noted in the eCRF. In addition, subjects receiving pulmonary rehabilitation prior to study entry should continue on the same schedule up to and including Week 24. Following Week 24, pulmonary rehabilitation may be adjusted per standard of care. Pulmonary rehabilitation may not be added to a subject's regimen between randomization and Week 24. Documentation of pulmonary rehabilitation should occur in the special circumstances section of the eCRF. Additional 6MWTs may be conducted as appropriate throughout the course of the study for the purposes of evaluating clinical worsening status.

Each 6MWT conducted after Randomization should be documented and compared to the subject's Baseline 6MWD. If a subject has a decrease of 15% or more in walk distance compared to Baseline, a second confirmatory 6MWT should be performed on a different day to assess for clinical worsening (confirmatory 6MWTs should be conducted within 30 days of the qualifying decrease in 6MWD; however, confirmatory 6MWTs occurring outside of this window will still be considered to have met the definition of clinical worsening and sent to the adjudication committee for review). If the second 6MWT also shows at least 15% decrease in 6MWD as compared to Baseline and the subject has either worsened in WHO Functional Class compared to Baseline or has the appearance or worsening of symptoms of right heart failure since Baseline, the subject will meet the 'disease progression' definition of clinical worsening and should follow steps as outlined in Section 3.2.1.1. Prior to exiting the study, the Study Drug Termination visit assessments should be conducted at the time the decision is made to discontinue study drug (prior to down titration). For subjects who meet the definition of clinical

worsening for disease progression due to at least a 15% decrease in 6MWD from Baseline, the date of the clinical worsening event will be the date of the second confirmatory 6MWT.

After the first 24 weeks of study participation, if a subject has any two consecutive 6MWTs on different days that demonstrate any decrease in 6MWD from Baseline accompanied with sustained WHO Functional Class III or IV symptoms for at least 24 weeks, consecutively, the subject will meet the clinical worsening definition of unsatisfactory long-term clinical response and should follow steps outlined in Section 3.2.1.1.

Details regarding the conduct of the 6MWT are described in Section 15.1.

3.2.1.3 *Borg Dyspnea Score*

The Borg dyspnea score will be assessed following each 6MWT. The Borg dyspnea score is a 10-point scale rating the maximum level of dyspnea experienced during the 6MWT (Section 15.1). Scores range from 0 (for the best condition) to 10 (for the worst condition).

3.2.1.4 *WHO Functional Classification*

The WHO functional classification for PAH (Section 15.2) will be assessed at Baseline prior to starting study drug and at all subsequent scheduled study visits, and every time the 6MWT is performed for purposes of assessing clinical worsening status.

3.2.1.5 *N-terminal pro-BNP*

Plasma NT-proBNP concentration is a useful biomarker for PAH as it is associated with changes in right heart morphology and function [Fijalkowska 2006]. NT-proBNP sample collection will occur at Baseline (prior to starting study drug), Week 12, Week 24, the first Continued Visit, and every other Continued Visit thereafter (i.e., Continued Visits #3, #5, #7, etc.). NT-proBNP will also be assessed at the Study Drug Termination visit.

3.2.1.6 *Right Heart Catheterization (Optional Assessment)*

This section describes the optional RHC assessments that may be conducted at Baseline and Week 24.

If a subject agrees to participate in the optional hemodynamic assessments, a RHC must be performed within 5 days before randomization (inclusive). The subject must be on stable

background therapy for a minimum of 10 days prior to this RHC. If a RHC is performed on the day of randomization, all other study-related assessments, other than initiation of study drug, should be performed prior to conduct of the RHC. A follow-up RHC must be performed within 72 hours following completion of Week 24 assessments. As best as possible, follow-up RHC should be performed within 3 to 6 hours of previous dose. Hemodynamic parameters to be assessed and recorded include heart rate (HR), systolic systemic arterial pressure (SAPs), diastolic systemic arterial pressure (SAPd), mean systemic arterial pressure (SAPm), systolic pulmonary artery pressure (PAPs), diastolic pulmonary artery pressure (PAPd), mean pulmonary artery pressure (PAPm), mean right atrial pressure (RAPm), mean pulmonary capillary wedge pressure (PCWPm), cardiac output (CO), arterial oxygen saturation (SaO₂), and mixed venous oxygen saturation (SvO₂). Additional hemodynamic parameters may also be calculated based on these measurements (e.g., pulmonary vascular resistance [PVR] and cardiac index [CI]). Weight and height will be collected to calculate body surface area (BSA) and index the cardiac output.

While this section describes the optional RHC assessments at Baseline and Week 24, all subjects eligible to participate in this study must either have data available from a historical RHC conducted within three years prior to the start of screening (i.e., date of signing the Informed Consent Form [ICF]), or undergo a RHC during the screening period prior to randomization with results consistent with the diagnosis of PAH as described in Section 4.1.

